APPENDIX III: Overactive Bladder Questionnaire (OABQ)

This questionnaire asks about how much you have been bothered by selected bladder symptoms during the past 4 weeks. Please circle the number that best describes the extent to which you were bothered by each symptom during the past 4 weeks. There are no right or wrong answers. Please be sure to answer every question.

During the past 4 weeks, how bothered were you by	Not at all	A little bit	Some what	Quite a bit	A great deal	A very great deal
Frequent urination during the daytime hours	1	2	3	4	5	6
An uncomfortable urge to urinate	1	2	3	4	5	6
3. A sudden urge to urinate with little or no warning	1	2	3	4	5	6
4. Accidental loss of small amounts of urine	1	2	3	4	5	6
5. Nighttime urination	1	2	3	4	5	6
6. Waking up at night because you had to urinate	1	2	3	4	5	6
7. An uncontrollable urge to urinate	1	2	3	4	5	6
8. Urine loss associated with a strong desire to urinate	1	2	3	4	5	6

The above questions asked about your feelings about individual bladder symptoms. For the following questions, please think about your overall bladder symptoms in the past 4 weeks and how these symptoms have affected your life. Please answer each question about how often you have felt this way to the best of your ability. Please circle the number that best answers each question.

During the past 4 weeks, how often have your bladder symptoms	None of the time	A little of the time	Some of the time	A good bit of the time	Most of the time	All of the time
9. Made you carefully plan your commute?	1	2	3	4	5	6
10. Caused you to feel drowsy or sleepy during the day?	1	2	3	4	5	6
11. Caused you to plan 'escape routes' to restrooms in public places?	1	2	3	4	5	6
12. Caused you distress?	1	2	3	4	5	6
13. Frustrated you?	1	2	3	4	5	6
14. Made you feel like there is something wrong with you?	1	2	3	4	5	6
15. Interfered with your ability to get a good night's rest?	1	2	3	4	5	6
16. Caused you to decrease your physical activities (exercising, sports, etc.)?	1	2	3	4	5	6
17. Prevented you from feeling rested upon walking in the morning?	1	2	3	4	5	6
18. Frustrated your family and friends?	1	2	3	4	5	6
19. Caused you anxiety or worry?	1	2	3	4	5	6
20. Caused you to stay home more often than you would prefer?	1	2	3	4	5	6
21. Caused you to adjust your travel plans so that you are always near a restroom?	1	2	3	4	5	6
22. Made you avoid activities away from restrooms (i.e., walks, running, hiking)?	1	2	3	4	5	6
23. Made you frustrated or annoyed about the amount of time you spend in the restroom?	1	2	3	4	5	6
24. Awakened you during sleep?	1	2	3	4	5	6
25. Made you worry about odor or hygiene?	1	2	3	4	5	6
26. Made you uncomfortable while traveling with others because of needing to stop for a restroom?	1	2	3	4	5	6
27. Affected your relationships with family and friends?	1	2	3	4	5	6
28. Caused you to decrease participating in social gatherings, such as parties or visits with family or friends?	1	2	3	4	5	6
29. Caused you embarrassment?	1	2	3	4	5	6
30. Interfered with getting the amount of sleep you needed?	1	2	3	4	5	6
31. Caused you to have problems with your partner or spouse?	1	2	3	4	5	6
32. Caused you to plan activities more carefully?	1	2	3	4	5	6
33. Caused you to locate the closest restroom as soon as you arrive at a place you have never been?	1	2	3	4	5	6

APPENDIX IV: 3-day voiding diary

VOIDING DIARY/UROLOGY

Version date: Amendment 5, June 29, 2016

This chart is a record of your voiding (urinating) and leakage (incontinence) of urine. Please complete this according to the following instructions prior to your visit to our office. Choose a 3 day period (if possible) to keep this record when you can conveniently measure your voids. If you are unable to keep the diary for a 24 hour period, try to keep it for as many hours as possible, say from early evening when you get home from work until you get up the next morning. Include all voids, even if they occur in the middle of the night.

EXAMPLE

VOIDING DIARY

TIME	AMOUNT VOIDED	ACTIVITY	LEAK VOLUME	URGE PRESENT	AMOUNT/TYPE OF INTAKE
6:45 AN 7:00AM		Awakening Turned on H2O	2	Yes	2 cups coffee 6 oz orange juice

Record the time of all voiding (you can use a kitchen measuring cup- 4 cup capacity), leakage, and intake of liquids. Measure all intake and output in ounces or mL (30mL - 1oz). Describe activity you were performing at the time of leakage. If you were not actively doing anything, record whether you were sitting, standing, or lying down. Estimate the amount of leakage according to the following:

0 = no leakage

- 1 = damp, few drops only
- 2 = wet underwear or pad
- 3 = soaked or emptied bladder

If the urge to urinate accompanied (or preceded) the urine leakage, write Yes. If you felt no urge when the leakage occurred, write No. Record the amount and type of all liquid intake using ounces or mL (30mL = 1oz) (1 cup = 8oz = 240mL).

DO NOT FILL OUT: RESEARCH PERSONNEL USE ONLY Bladder diary Page 1 of 7	Participant Identifier
	Data entry initials Data entry date

Page - 80 - of 96

D	$\Delta \mathbf{V}$	#1 :	RI	ΔD	DER	DIA	RV

date /	′ /	(\mathbf{mm}/\mathbf{e})	dd/	vvvv)

- Please fill out for all urination episodes beginning with when you wake up, up until the next day when you wake up. Use the back if necessary
- Please also circle time when you went to bed, and when you woke up, for each day (for 3 days).

. Follow the example as a guide

• Follow	the example as a	guide						
TIME	AMOUNT VOIDED	ACTIVITY	VC	AK OLUI rcle)	ИE		URGE PRESENT (circle)	AMOUNT/TYPE OF INTAKE
			0	1	2	3	Yes / No	
			0	1	2	3	Yes / No	
			0	1	2	3	Yes / No	
			0	1	2	3	Yes / No	
			0	1	2	3	Yes / No	
			0	1	2	3	Yes / No	
			0	1	2	3	Yes / No	
			0	1	2	3	Yes / No	
			0	1	2	3	Yes / No	
			0	1	2	3	Yes / No	
			0	1	2	3	Yes / No	
			0	1	2	3	Yes / No	
			0	1	2	3	Yes / No	
			0	1	2	3	Yes / No	
			0	1	2	3	Yes / No	
			0	1	2	3	Yes / No	
			0	1	2	3	Yes / No	
			0	1	2	3	Yes / No	
			0	1	2	3	Yes / No	
			0	1	2	3	Yes / No	
			0	1	2	3	Yes / No	
			0	1	2	3	Yes / No	
			0	1	2	3	Yes / No	
			0	1	2	3	Yes / No	
-								+

DO NOT FILL OUT: RESEARCH PERSONNEL USE ONLY Bladder diary	Desiring Library	
Page 2 of 7	Participant Identifier	
	Data entry initials Data entry date	

DAY #1: BLADDER DIARY cont.

TIME	AMOUNT VOIDED	ACTIVITY	LEAK VOLUME	URGE PRESENT	AMOUNT/TYPE OF INTAKE
			(circle)	(circle)	
			0 1 2 3	Yes / No	
			0 1 2 3	Yes / No	
			0 1 2 3	Yes / No	
			0 1 2 3	Yes / No	
			0 1 2 3	Yes / No	
			0 1 2 3	Yes / No	
			0 1 2 3	Yes / No	
			0 1 2 3	Yes / No	
			0 1 2 3	Yes / No	
			0 1 2 3	Yes / No	
			0 1 2 3	Yes / No	
			0 1 2 3	Yes / No	
			0 1 2 3	Yes / No	
			0 1 2 3	Yes / No	
			0 1 2 3	Yes / No	
			0 1 2 3	Yes / No	
			0 1 2 3	Yes / No	
			0 1 2 3	Yes / No	
			0 1 2 3	Yes / No	
			0 1 2 3	Yes / No	
			0 1 2 3	Yes / No	
			0 1 2 3	Yes / No	
			0 1 2 3	Yes / No	
			0 1 2 3	Yes / No	
			0 1 2 3	Yes / No	
			0 1 2 3	Yes / No	-
			0 1 2 3	Yes / No	
			0 1 2 3	Yes / No	
			0 1 2 3	Yes / No	
			0 1 2 3	103 / 110	

DO NOT FILL OUT: RESEARCH PERSONNEL USE ONLY Bladder diary	Detident 13 of 6
Page 3 of 7	Participant Identifier
	Data antry initials - Data entry data

DAY #2: BLADDER DIARY

date// (mm/dd/yyyy)

- Please fill out for all urination episodes beginning with when you wake up, up until the next day when you wake up. Use the back if necessary
- Please also circle time when you went to bed, and when you woke up, for each day (for 3 days).

• Follow the example as a guide

 Follow the 	e example as a gui							
TIME	AMOUNT VOIDED	ACTIVITY	VO	AK LUN cle)	ИE		URGE PRESENT (circle)	AMOUNT/TYPE OF INTAKE
			0	1	2	3	Yes / No	
			0	1	2	3	Yes / No	
			0	1	2	3	Yes / No	
			0	1	2	3	Yes / No	
			0	1	2	3	Yes / No	
			0	1	2	3	Yes / No	
			0	1	2	3	Yes / No	
			0	1	2	3	Yes / No	
			0	1	2	3	Yes / No	
			0	1	2	3	Yes / No	
			0	1	2	3	Yes / No	
			0	1	2	3	Yes / No	
			0	1	2	3	Yes / No	
			0	1	2	3	Yes / No	
			0	1	2	3	Yes / No	
			0	1	2	3	Yes / No	
			0	1	2	3	Yes / No	
			0	1	2	3	Yes / No	
			0	1	2	3	Yes / No	
			0	1	2	3	Yes / No	
			0	1	2	3	Yes / No	
			0	1	2	3	Yes / No	
			0	1	2	3	Yes / No	
			0	1	2	3	Yes / No	
			0	1	2	3	Yes / No	

DO NOT FILL OUT: RESEARCH PERSONNEL USE ONLY		
Bladder diary		
•	Participant Identifier	
Page 4 of 7	•	

Data entry initials Data entry date

DAY #2: BLADDER DIARY cont.

TIME	AMOUNT VOIDED	ACTIVITY	LEAK VOLUME (circle)	URGE PRESENT (circle)	AMOUNT/TYPE OF INTAKE
				3 Yes / No	
			0 1 2	3 Yes / No	
			0 1 2	3 Yes / No	
			0 1 2	3 Yes / No	
			0 1 2	3 Yes / No	
			0 1 2	3 Yes / No	
			0 1 2	3 Yes / No	
			0 1 2	3 Yes / No	
			0 1 2	3 Yes / No	
			0 1 2	3 Yes / No	
			0 1 2	3 Yes / No	
			0 1 2	3 Yes / No	
			0 1 2	3 Yes / No	
			0 1 2	3 Yes / No	
			0 1 2	3 Yes / No	
			0 1 2	3 Yes / No	
			0 1 2	3 Yes / No	
			0 1 2	3 Yes / No	
			0 1 2	3 Yes / No	
			0 1 2	3 Yes / No	
				3 Yes / No	
				3 Yes / No	
				3 Yes / No	
			0 1 2	3 Yes / No	
				3 Yes / No	
				3 Yes / No	
				3 Yes / No	
			0 1 2	3 Yes / No	
				3 Yes / No	
			0 1 2	3 Yes / No	

DO NOT FILL OUT: RESEARCH PERSONNEL USE ONLY	
Bladder diary	

Page 5 of 7

Participant Identifier

DAY	# 3:	BLAD	DER	DIARY

_						_
date /	' /	mm	dd	/ v	V	VV)

- · Please fill out for all urination episodes beginning with when you wake up, up until the next day when you wake up. Use the back if necessary
- Please also circle time when you went to bed, and when you woke up, for each day (for 3 days).

Follow the example as a guide

VOIDED	ACTIVITY	VC	AK OLUN rcle)			URGE PRESENT (circle)	AMOUNT/TYPE OF INTAKE
		0	1	2	3	Yes / No	
		0	1	2	3	Yes / No	
		0	1	2	3	Yes / No	
		0	1	2	3	Yes / No	
		0	1	2	3	Yes / No	
		0	1	2	3	Yes / No	
		0	1	2	3	Yes / No	
		0	1	2	3	Yes / No	
		0	1	2	3	Yes / No	
		0	1	2	3	Yes / No	
		0	1	2	3	Yes / No	
		0	1	2	3	Yes / No	
		0	1	2	3	Yes / No	
		0	1	2	3	Yes / No	
		0	1	2	3	Yes / No	
		0	1	2	3	Yes / No	
		0	1	2	3	Yes / No	
		0	1	2	3	Yes / No	
		0	1	2	3	Yes / No	
		0	1	2	3	Yes / No	
		0	1	2	3	Yes / No	
		0	1	2	3	Yes / No	
		0	1	2	3	Yes / No	
		0	1	2	3	Yes / No	
		0	1	2	3	Yes / No	

			0	1	2	3	Yes	/	No		
DO NOT FILL OUT Bladder diary Page 6 of 7	T: RESEARCH PERSON	NNEL USE ONLY		Partic	ipant Id	lentific	er		_		
			i	Data e	ntry in	itials	Data e	ntry o	late		

DAY #3: BLADDER DIARY cont.

TIME	AMOUNT VOIDED	ACTIVITY	LEAK VOLUME	URGE PRESENT	AMOUNT/TYPE OF INTAKE
			(circle) 0 1 2	(circle) 3 Yes / No	
			0 1 2	3 Yes / No	
			0 1 2	3 Yes / No	
			0 1 2	3 Yes / No	
				3 Yes / No	
			0 1 2	3 Yes / No	
				3 Yes / No	
			0 1 2	3 Yes / No	
			0 1 2	3 Yes / No	
			0 1 2	3 Yes / No	
			0 1 2	3 Yes / No	
			0 1 2	3 Yes / No	
			0 1 2	3 Yes / No	
			0 1 2	3 Yes / No	
			0 1 2	3 Yes / No	
			0 1 2	3 Yes / No	
			0 1 2	3 Yes / No	
			0 1 2	3 Yes / No	
			0 1 2	3 Yes / No	
			0 1 2	3 Yes / No	
			0 1 2	3 Yes / No	
			0 1 2	3 Yes / No	
			0 1 2	3 Yes / No	
			0 1 2	3 Yes / No	
			0 1 2	3 Yes / No	
			0 1 2	3 Yes / No	
			0 1 2	3 Yes / No	
			0 1 2	3 Yes / No	
			0 1 2	3 Yes / No	
			0 1 2	3 Yes / No	

DO NOT FILL OUT: RESEARCH PERSONNEL USE ONLY Bladder diary	
Page 7 of 7	Participant Identifier

Data entry initials Data entry date

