3.3 Inclusion Criteria

- 1. Aged 25-80 at screening. Subjects older than 80 will be allowed at the discretion of the PI.
- 2. Ambulatory (defined as able to ambulate at least 10 meters, with or without assistance).
- 3. Clinical Diagnosis of PD based on the United Kingdom Brain Bank diagnostic criteria for PD.²⁸
- 4. At baseline visit (Visit 2) patients must have:
 - a. At least 8 micturitions per 24 hours and
 - b. At least 3 urgency episodes per 3-day diary.
- 5. A MoCA score between 19 and 28 (inclusive) at screening. For those on cognitive enhancers (donepezil, rivastigmine, memantine, galantamine) a MoCA score between 19 and 29 (inclusive) at screening.
- 6. Provide informed consent to participate in the study and understand that they may withdraw their consent at any time without prejudice to their future medical care.

- 7. Be cognitively capable, in the opinion of investigator, to understand and provide such informed consent.
- 8. Be cognitively capable to complete the required questionnaires and assessments, OR have a care partner who is willing and capable to assist them in the completion of these tasks.
- 9. Be on a stable regimen of antiparkinson's medications at least 30 days prior to screening, and be expected to remain on a stable dose for the duration of the study.
- 10. If taking cognitive enhancers (donepezil, rivastigmine, memantine, galantamine), must be on stable dose at least 30 days prior to screening, and be expected to remain on a stable dose for the duration of the study.

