3.10.2 Procedures related to secondary end points

3.10.2.1 Overactive Bladder Questionnaire (OABQ – Appendix III)

Overactive bladder (OAB) is characterized by symptoms of urinary frequency and urgency, with and without incontinence. The Overactive Bladder Questionnaire³³ (OABQ) is a 33-item, self-administered instrument that contains a symptom bother scale (8 items to be administered during visits 1, 3, 5, 6, and 7) and a health-related quality of life scale (HRQL-to be administered during visits 3 and 7), pertaining to OAB symptoms

impact on HRQL. The OABQ was developed from an initial version of 62 items to its final form and has been shown to be a valid and reliable instrument in distinguishing normal from clinically diagnosed continent and incontinent patients. In addition to measuring the severity of symptom bother, the OABQ is also useful in quantifying the negative impact of both continent and incontinent symptoms on HRQL. This instrument has been used as an efficacy outcome in the pivotal randomized clinical trials of mirabegron, and the drug's efficacy was indeed accurately reflected in the instrument. The OABQ has also been studied and found useful in PD. ³⁴

3.10.2.2 3-Day Voiding Diary (Appendix IV)

A 3-day voiding diary will be implemented to collect additional efficacy measures of average daily incontinence episodes, micturition frequency, and volume voided per micturition. Subjects will be trained in the diary completion. A toilet hat will be supplied for volume measurement. Subjects are instructed to record the times of every voiding event during three consecutive days; amount voided with each event; instances of leaking including incontinence; whether there was associated urge to void with any voiding event; and, whether they had to get out of bed to void.

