7.4.2 Summary of efficacy data

The first secondary objective of this project is to assess the efficacy of mirabegron for treating OAB symptoms in PD with CI. The hypothesis is that participants in the

treatment group will experience improved OAB symptoms compared to placebo group. As this is a superiority objective, a 2-sample t-test or the Mann-Whitney-Wilcoxon test will be used as appropriate to determine significant differences between treatment groups on change in OABQ subscale scores from visit 3 to visit 7. Other measures of OAB symptoms (including PPBC and the average daily values from the diary) will follow similar analyses.

The rest of the secondary objectives are to assess efficacy of mirabegron in PD and the impact of mirabegron on other non-motor symptoms in PD including health related quality of life and excessive daytime sleepiness in PD patients with OAB symptoms and CI. The related hypotheses are that mirabegron will not impact these non-motor symptoms. The goal is to demonstrate equivalent non-motor symptoms prior to and following treatment with mirabegron as well as change compared to the placebo group. Tests of equivalence will be performed using the two one-sided tests approach on change from visit 3 to visit 7 in related variables within groups as well as between the two groups. Equivalence ranges will be determined for each measure based on available literature prior to data analysis.

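### The diary cover page permits part-day recording, against its own day pages and section 3.10.2.2, and no rule says how a part-day counts towards the per-24-hour entry criterion and the average-daily endpoints

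*Combined protocol and SAP*

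**What the plan says.** The diary in Appendix IV gives two different instructions.

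- **Cover page.** "If you are unable to keep the diary for a 24 hour period, try to keep it for as many hours as possible", followed by the example "say from early evening when you get home from work until you get up the next morning". Three days are themselves optional: "Choose a 3 day period (if possible) to keep this record when you can conveniently measure your voids".
- **Day pages, repeated for each of the three days.** "Please fill out for all urination episodes beginning with when you wake up, up until the next day when you wake up". Patients also mark when they went to bed and when they woke.

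Section 3.10.2.2 sides with the day pages: "Subjects are instructed to record the times of every voiding event during three consecutive days".

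The uses made of the diary presuppose whole days. In section 3.3, inclusion 4a reads "At least 8 micturitions per 24 hours and" is joined to 4b, "At least 3 urgency episodes per 3-day diary". Section 3.10.2.2 names average daily incontinence episodes and micturition frequency, plus volume per micturition, as efficacy measures. Section 7.4.2 tests change from Visit 3 to Visit 7 between arms in the OABQ subscales, and adds: "Other measures of OAB symptoms (including PPBC and the average daily values from the diary) will follow similar analyses".

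No section sets a minimum number of hours or days, names the denominator of the daily average, or scales a part-day to 24 hours. Section 7.4 says missing data are not imputed, but not whether a part-recorded day is missing.

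**The concern.** A patient who follows the cover page hands in a count covering perhaps half a day, and the plan then needs a per-day figure from it. The analyst has to choose between using the count as it stands, scaling it up, and dropping the day. Each choice gives a different answer, and none is pre-specified.

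Incomplete diaries are foreseeable in this population. Everyone enrolled is meant to have impaired cognition, and inclusion 8 admits patients who need a care partner to help complete assessments.

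Two things are at stake. At Visit 2, a patient who meets 4a over whole days could be screened out. At Visits 3 and 7, the daily averages become noisier, and they become biased if part-day use differs between arms.

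**Working it through.** **Inputs from the documents.** The clinical studies section of the prescribing information in Appendix I gives baseline micturitions of 11.48 to 11.80 per 24 hours. Its differences from placebo are -0.60, -0.61, -0.47 (25 mg) and -0.42 (50 mg, Study 3). The protocol sets no target effect of its own. Section 7.1 gives 20 active and 10 placebo patients.

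**Reproducing the label differences.** Mirabegron change minus placebo change:
- Study 1: -1.93 + 1.34 = -0.59 (stated -0.60; rounding)
- Study 2: -1.66 + 1.05 = -0.61
- Study 3, 25 mg: -1.65 + 1.18 = -0.47
- Study 3, 50 mg: -1.60 + 1.18 = -0.42

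**Assumptions.** A part-day covers 12 to 14 hours, voids are spread evenly over the day, one day in three is affected, and the raw count is averaged as a full day.

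**Loss for one patient.** Loss in the 3-day mean = baseline × (24 − h) / 24 / 3.
- 12 h: 11.65 × 12/24 / 3 = 1.94
- 13 h: 11.65 × 11/24 / 3 = 1.78
- 14 h: 11.65 × 10/24 / 3 = 1.62
- Across baselines 11.48 to 11.80: 1.59 to 1.97

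**Uneven voiding.** If the recorded window holds a share s of the day's voids, the loss is 11.65 × (1 − s) / 3:

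| s | loss in 3-day mean |
|---|---|
| 40% | 2.33 |
| 60% | 1.55 |
| 80% | 0.78 |
| 90% | 0.39 |

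**Eligibility, if 4a is applied to the 3-day mean.** A patient truly at 9 per day with one 12-hour day shows (9 + 9 + 4.5)/3 = 7.5. With 14 hours the figure is (9 + 9 + 5.25)/3 = 7.75. The true rate below which one part-day pushes the mean under 8 is 8 / (1 − (24 − h)/72), which is 9.6 at 12 h and 9.3 at 14 h.

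**Treatment comparison.** False difference = loss per affected patient × difference between arms in the share affected at Visit 7. A 20-point gap at 12 h gives 0.20 × 1.94 = 0.39, below every label effect. The gap needed to equal 0.42 to 0.61 is:
- 12 h: 0.42/1.94 = 22% to 0.61/1.94 = 31%
- 13 h: 0.42/1.78 = 24% to 0.61/1.78 = 34%
- 14 h: 0.42/1.62 = 26% to 0.61/1.62 = 38%

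**How easily chance produces such a gap.** The documents give no part-day rate. Suppose 20% of patients in both arms have one part-day (range 10% to 30%). By exact binomial with 20 and 10 patients, the observed shares differ by at least 20 points in about 26% of trials (13% to 33%), and by at least 24 points in about 14% (5% to 21%).

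**Against the precision of the endpoint.** The label's confidence intervals and group sizes imply a change SD of about 2.4 to 2.8. For Study 1, (0.90 − 0.29)/2/1.96 = 0.156, and 0.156/√(1/480 + 1/473) = 2.4. With 20 and 10 patients the standard error is SD × √(1/20 + 1/10), about 0.9 to 1.1 voids. A bias of 0.39 is under half of that.

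**The case against.** The cover sentence is a fallback for patients who cannot manage 24 hours, not the main instruction. The day pages and section 3.10.2.2 ask for full days, section 3.9.1 schedules diary training and a concordance check at screening, and section 7.4 requires checks for inconsistent and missing data. Void times are recorded, so a part-day can be seen. All of this stands, and it should make part-days less common. None of it says what to do with one. Rescaling by hours is not provided for, and evening-to-morning hours need not represent the whole day.

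A reader might infer that the plan instructs the analyst to average a half-recorded day as a full one. It does not. The plan is silent, and that treatment is an assumption of the arithmetic. Likewise, 4a does not say it is judged on a 3-day mean; the patient in the example records 9 voids on each complete day.

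A reader might also set the loss of 1.6 to 2.0 voids beside the label effect of 0.42 to 0.61 and conclude that the treatment difference could be wrong by more than the drug effect. That does not follow. The first figure is one patient's shortfall; the second is a difference between arm means. Part-days equally common in both arms and at both visits largely cancel in the change from Visit 3 to Visit 7. The trial is randomised and double-blind, and the documents give no reason for part-day use to differ by arm other than chance.

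Finally, the diary is one of the other measures under a secondary objective, in a 30-patient pilot with limited precision for an effect of this size. That limits the consequence but does not remove the contradiction.

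**Conclusion.** The contradiction is real and sits in the current text: one cover-page sentence permits what the day pages and section 3.10.2.2 do not, and no rule deals with the result. Under the stated assumptions, one part-day in three costs the affected patient about 1.6 to 2.0 voids in the daily mean, or 0.4 to 2.3 as the recorded window holds 90% down to 40% of the day's voids. It can also take a patient truly at 9 per day below the entry threshold.

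For the treatment comparison the effect is mainly added noise. Bias requires unequal part-day use, and reaching the label effect takes a gap of roughly 22 to 34 points for 12 to 13 recorded hours (up to 38 at 14 hours). With only 10 placebo patients, chance could produce a gap towards the lower end of that range, but how often depends on a part-day rate the documents do not give. Screening and a secondary efficacy measure are affected; the MoCA primary endpoint is not.

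**What to change.** - Delete the part-day sentence and its example from the cover page, and make three days a requirement there, so that the form agrees with its day pages and section 3.10.2.2.
- State in section 7 that only complete wake-to-wake days count, and that the daily average divides by the number of complete days.
- Pre-specify the minimum number of complete days for a diary to enter the analysis (for example 2 of 3), before unblinding.
- For Visit 2 eligibility, repeat an incomplete diary, so that 4a and 4b are both applied to a full three-day record. A two-day minimum would leave 4b undefined.

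The cost is wording on the form and in section 7. A few diaries will be repeated or become missing. With no imputation, each one lost in the placebo arm is 10% of that arm's diary data, which is a reason to favour repeating a diary over discarding it.
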